- j. For subjects in the observational period, the following concomitant medications will be collected: DMARDs, including any immunosuppressives or anti-TNFs and/or other immunosuppressive biologic agents; corticosteroids; and anti-infective agents taken for medically important infections. Only non-drug treatments received due to an adverse event will be collected.
- k. Weight will be measured at every visit for subjects who are < 18 years of age and who weigh ≤ 62 kg. For those subjects who are ≥ 18 years of age or weigh > 62 kg, weight will be measured annually as part of the physical examination.
- l. Tanner Stage Assessment will be performed annually for subjects < 18 years of age or who have a score of < 5 on 1 or more applicable domain(s). The Tanner Stage Assessment does not need to be repeated at the early withdrawal visit if it was performed within 2 months before the visit.
- m. Additional laboratory testing may be performed according to local guidelines or standard of care and for follow-up of abnormal laboratory test results.
- n. The evaluation of childbearing potential in female subjects must be documented in the subject's source documents.
- o. Urine pregnancy tests will be performed at each of the visits in the active treatment period for all female subjects who, in the opinion of the investigator, are of childbearing potential; this includes subjects who are menstruating at the time of the visit. The baseline pregnancy test must be performed within 7 days before the baseline visit. Pregnancy tests will also be done whenever a menstrual cycle is missed during the active treatment period or when potential pregnancy is otherwise suspected. Pregnancy tests may also be repeated as per request of IRB/IECs or if required by local regulations.
- p. Discussion of sexual activity and use of contraception must be documented in the subject's source documents.
- q. Assessment will be completed by the subject's parent or legal representative/guardian for subjects aged < 18 years, or directly by subjects aged ≥ 18 years at the time of the assessment.
- r. Childhood Health Assessment Questionnaire (CHAQ) will be completed by the subject's parent or legal representative/guardian for subjects aged < 18 years at the time of the assessment; Health Assessment Questionnaire (HAQ) will be completed directly by subjects aged ≥ 18 years at the time of the assessment.

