7.1. Safety Assessments

For subjects in the active treatment period, and the withdrawal/re-treatment period, safety will be assessed using the following measures:

1. Physical examinations will be performed by a physician. Any clinically significant abnormalities or worsening of medical history conditions should be recorded on the source documents and the appropriate adverse event CRF.
 - The physical examination will include the Tanner Stage Assessment for subjects <18 years of age or who have a score of <5 on 1 or more applicable domain(s). The sexual maturity rating of each subject will be determined according to the criteria adapted from Tanner. Female subjects will be classified on a scale of 1 to 5 across the following 2 maturity domains: breast and pubic hair characteristics. Male subjects will be classified on a scale of 1 to 5 across the following 3 maturity domains: pubic hair, penis and testes characteristics.
2. Vital sign measurements will include temperature, blood pressure and pulse rate (after sitting for at least 5 minutes).
 - A sitting blood pressure will be obtained by qualified site personnel and should be taken using the same arm throughout the study. If possible, a different arm should be used for the collection of blood samples.
3. Height and Weight.
4. Subjects will be evaluated for adverse events (infectious and noninfectious), serious adverse events, malignancy, and medically important infections.

- Infectious and noninfectious adverse events will be recorded on separate CRFs.
 - Medically important infections are defined as infections that require parenteral anti-infective agents (IV, IM) and/or hospitalization.
 - Infections considered preventable by vaccination will be reported on the infectious adverse event CRF.
5. Injection site reactions (symptoms, action taken, number, and frequency) will be monitored throughout the study and will be graded for intensity according to the Symptom Occurrence Scale (Itching, Redness, Swelling, Pain, Ulceration). Injection site reactions need to be clearly differentiated from symptoms associated with the technique of administering subcutaneous injections (eg, physical injury to blood vessels).
6. Clinical laboratory evaluations including blood chemistry, hematology, and urinalysis.

For subjects in the observational period, safety will be assessed through collection of the following information via telephone contact:

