2.2. Study Design

2.2.1. Basic Features of the Study Design

This is an open-label, single treatment, multi-center, 8-year extension study in pediatric subjects who have been diagnosed with one of 3 subtypes of JIA (eoJIA, ERA, or PsA), have received at least one dose of etanercept and completed approximately 96 weeks of participation in study 0881A1-3338-WW (B1801014). These subjects will be asked to participate in study B1801023. It is anticipated that approximately 100 subjects will be enrolled in study B1801023. This 96-month study contains 3 periods: an active treatment period, a withdrawal/re-treatment period, and an observational period.

Active treatment period

Subjects who completed approximately 96 weeks of active treatment with investigational product (etanercept) in study 0881A1-3338-WW (B1801014) and are eligible to continue investigational product in study B1801023 will enter directly into the active treatment period. These subjects may continue to receive investigational product for up to 8 additional years (96 months).

Withdrawal/Re-treatment period

Withdrawal: Subjects who have either completed approximately 96 weeks of treatment in study 0881A-3338 or were enrolled in the active treatment period of study B1801023 and who have either met the Wallace definition for clinically inactive disease for at least 6 months on investigational product (etanercept) or who, in the investigators judgment, have had a good clinical response and would benefit from withdrawal from investigational product and are otherwise eligible can enter the withdrawal/re-treatment period. However, the withdrawal/re-treatment period is optional and it is ultimately up to the investigator and subject to determine when the subject should be withdrawn from treatment.

Re-treatment: Subjects requiring re-treatment per the investigator's clinical judgment and who are otherwise eligible will be offered the option to re-start treatment with investigational product.

Subjects may not enter the withdrawal/re-treatment period more than once during the study.

Observational period

All subjects will be followed for a total of 8 years from the time of initial entry into the study as follows:

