Tanner Stage Assessment for subjects <18 years of age or who have a score of <5 on 1 or more applicable domain(s). The Tanner Assessment does not need to be repeated if it was performed within 2 months before the early withdrawal visit.

Vital Signs: Temperature, blood pressure (mmHg) and pulse rate (beats/min, after sitting for at least 5 minutes);

Growth parameters: height, weight, BMI;

- Efficacy:
 - *ACR Pediatric 30, 50, 70, 90, and 100, defined as $\geq 30\%$ (and 50%, 70%, 90%, 100%, respectively) improvement from baseline in at least 3 of the 6 following variables, with no more than 1 of the remaining variables worsening by $> 30\%$:*
 - *Physician's Global Assessment (PGA) of Disease Activity on a 21-circle visual analogue scale (VAS);*
 - *Patient/Parent Global Assessment on a 21-circle VAS;*
 - *Childhood Health Assessment Questionnaire (CHAQ)*

- *Number of joints with active arthritis, defined as joints that are swollen or, in the absence of swelling, joints with limited range of motion accompanied by pain and/or tenderness;*
- *Number of joints with limited range of motion;*
- *Laboratory measure of inflammation, c-reactive protein (CRP);*

(Note: ACRPedi responses will be calculated based on parent study baseline. For subjects aged ≥ 18 years, CHAQ is missing)

- *Individual components of the ACR Pediatric Assessments;*
- *Pain Assessment on a 21-circle VAS;*
- *Duration of morning stiffness in minutes;*
- *Clinically inactive disease defined as follows per 2011 Wallace Criteria:*
 - *No joints with active arthritis (defined as joints that are swollen or, in the absence of swelling, joints with limited range of motion accompanied by pain and/or tenderness);*
 - *No fever, rash, serositis, splenomegaly, or generalized lymphadenopathy attributable to JIA;*
 - *No active uveitis;*
 - *CRP level within normal limits in the laboratory where tested or, if elevated, not attributable to JIA;*
 - *PGA of disease activity score of best possible on the scale used;*
 - *Duration of morning stiffness of ≤ 15 minutes;*
- *The Juvenile Arthritis Disease Activity Score (JADAS), using 4 components (PGA of Disease Activity, Patient/Parent Global Assessment, number of joints with active arthritis and CRP).*

- *Additional Secondary Endpoints for ERA Subjects*
 - *Overall Back Pain and Nocturnal Back Pain on a 100 mm VAS;*

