5.7. Laboratory, Vital Signs, Tanner Stage Assessment

For laboratory data, vital sign measurements and other continuous safety data, the number of observations, mean, standard deviation, median, minimum, maximum will be summarized by visit. Height, weight, BMI, and Tanner scores will be summarized using the number of observations, mean, standard deviation, median, minimum, and maximum by age group (ages 2-4, 5-11 and 12-17 years at start of parent study). The visits shown in these reports will be the baseline visit from the parent study, weeks 12, 24, 48, and 96, from the parent study and all visits from the extension study where

the data is collected. Some additional analyses of the Tanner data that takes age at time of measurement into account may also be done.

The Potentially Clinically Important (PCI) Flag is a derived flag value based on the PCI criteria defined for laboratory data captured in the study. The PCI criteria are based on NCI toxicity criteria. The number (%) of subjects with PCI events will also be provided for the lab data.

These summaries will be performed for FAS (active period (both parent and extension studies)), WAS, and RTAS.

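### Tanner means by visit in the 12-17 age group run low because subjects aged 18 or over who have completed maturation stop being assessed and are not counted

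*SAP*

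**What the plan says.** Who is assessed: in the Protocol's Schedule of Activities for the active treatment period, footnote l reads "Tanner Stage Assessment will be performed annually for subjects < 18 years of age or who have a score of < 5" on at least one applicable domain. The withdrawal and re-treatment schedules carry the same footnote, and SAP 4.2.2 repeats the rule in the endpoint definition. The scale tops out at 5; Protocol 7.1 states for girls that "Female subjects will be classified on a scale of 1 to 5", and boys are scored on the same range.

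How it is summarised: SAP 5.7 says "Tanner scores will be summarized using the number of observations, mean, standard deviation, median, minimum, and maximum by age group", with groups defined as "ages 2-4, 5-11 and 12-17 years at start of parent study". On timing it says "The visits shown in these reports will be the baseline visit from the parent study, weeks 12, 24, 48, and 96, from the parent study", followed by every extension visit at which data are collected. The same summaries are made for the active period, the withdrawal set and the re-treatment set.

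Missing values: SAP 5.16 leaves a value that is still missing after derivation as missing. No rule carries stage 5 forward. SAP 5.7 allows, but does not require or specify, further Tanner analyses that use age at measurement.

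**The concern.** Whether a subject aged 18 or over has a Tanner score depends on the score itself. Someone complete on every domain leaves the table, and someone still below 5 on any domain stays. Because the groups are fixed at parent-study start, the 12-17 group ages through this threshold during the extension, and its by-visit mean is taken over an increasingly selected remainder.

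Tanner stage is a listed secondary endpoint in a study whose secondary objectives include long-term safety. An observed mean that is too low looks like slower maturation, which is the adverse direction. The table prints the number of observations, so a reader can see it shrink, but nothing says that completed puberty is the reason.

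**Working it through.** The documents give no figure on this point, so there is none to reproduce. The timing follows from their own numbers; the size needs assumptions.

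**Step 1: when the group passes 18.** SAP 2.2.1 describes "Subjects who completed approximately 96 weeks of active treatment with investigational product" before the extension. 96 weeks = 96 × 7 / 30.4375 = 22.08 months. The youngest member of the group is 12.0 years at parent start and turns 18 after 72 months, so at extension Month 72 − 22.08 = 49.9. Adding the 6-week maximum gap from last parent dose to extension baseline (Protocol 6.1.1.1) gives 102 weeks = 23.46 months and Month 48.5. Tanner assessment is annual (Months 12, 24 and so on to 96), so the first visit at which the whole group is 18 or older is Month 60.

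**Step 2: share of the group aged 18 or over.** Assume start ages uniform on 12 to 18, since the documents give no distribution, and no gap. At Month m, subjects who started above the cut-off 18 − (m + 22.08)/12 are now 18 or older, and the share is (18 − cut-off)/6, capped at 1. For Month 12 the cut-off is 15.16 and the share is 2.84/6 = 47%.

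| Extension month | 0 | 12 | 24 | 36 | 48 | 60-96 |
|---|---|---|---|---|---|---|
| Aged 18 or over | 31% | 47% | 64% | 81% | 97% | 100% |

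The oldest members of the 5-11 group are just under 12 at the start, so they reach 18 at about Month 50. With uniform ages 5 to 12, 12% of that group is 18 or over at Month 60 and 55% at Month 96. In the withdrawal and re-treatment sets visits are counted from entry to those periods, so the threshold comes at or before about Month 50 on those clocks.

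**Step 3: size of the shortfall.** This is a simulation of one domain, with 400,000 subjects. Age at stage 5 is taken as Normal with (mean, SD) of (15, 1.2), (15.5, 1.2), (16, 1.5) or (16.5, 1.5) years, and each earlier stage lasts 1.0 or 1.2 years. A subject is assessed if under 18, or if the score one year earlier was below 5. The shortfall is the mean over all subjects minus the mean over those assessed.

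| Extension month | Shortfall (stages) |
|---|---|
| 12 | about 0.1 to 0.4 |
| 24 | about 0.06 to 0.4 |
| 36 | about 0.02 to 0.3 |
| 60 | about 0.1 to 0.3, with under 3% of the group due assessment |

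At Month 60, with 1.2 years per stage, the four scenarios give means among those assessed of 4.92, 4.93, 4.77 and 4.72, against 4.99 to 5.00 for everyone. A Month 0 shortfall arises only if the parent study used the same assessment rule, which these documents do not show.

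**Step 4: sensitivity to the eligibility rule.** If eligibility were decided by the score at the current visit, the Month 60 mean would be about 3.8 to 4.0 against 5.0, on under 1% of the group. That score is not known until it is taken, so the last recorded score is the ordinary reading.

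**The case against.** The strongest reply is that the late cells are nearly empty. Enrolment is about 100 across all ages, so under 3% at Month 60 is at most two or three subjects even if everyone were in this age group. A descriptive mean on so few, with its count beside it, would mislead few readers. This stands for Month 60 onward. It does not answer Months 12 to 24, where roughly half to a third of the group (53% and 36%, the complement of the shares in Step 2) is still under 18 and due assessment, and the table will be read.

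Second, the by-age analysis mentioned in SAP 5.7 has no outcome-dependent loss below 18, because every subject under 18 is due assessment whatever the stage. That also stands. But the analysis is optional and unspecified, and from 18 upward it has the same selection.

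Third, carrying stage 5 forward without limit would create the opposite bias: subjects leaving a period at stage 5 would stay in its mean while those leaving at stage 3 or 4 would not. This is right, and the carry-forward must stop when the subject leaves the period.

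Fourth, neither document says that the endpoint tests an effect of treatment on puberty, and no hypothesis or decision rests on it. That limits how much hangs on the table.

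A reader might also infer that after about Month 50 every score in the group is below 5 by construction, that the mean is a full stage too low, or that the table would show maturation regressing. The documents support none of these. A subject last scored 4 can score 5 at the current visit and is counted once. Retention needs only one domain below 5, so other domains can contribute 5s. The full-stage gap requires eligibility to depend on the current score. Under the last-score rule no scenario falls by more than about 0.06 between visits, and with (16.5, 1.5) and 1.2 years per stage the mean rises from 3.84 at Month 0 to 4.72 at Month 60.

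**Conclusion.** The point holds as a downward bias that the plan's own rules create. In the 12-17 group the by-visit Tanner mean is too low by about 0.05 to 0.4 stage at Months 12 to 24. From about Month 50, with Month 60 the first full visit, the only subjects due assessment are those below 5 on some domain last time, and the shortfall is about 0.1 to 0.3 stage on under 3% of the group. The 5-11 group begins to be affected between about Months 50 and 60.

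The timing rests on document figures. The sizes rest on assumed ages at stage 5, uniform start ages, 1.0 to 1.2 years per earlier stage, a single domain, and eligibility decided by the last recorded score; the footnote does not say which assessment it means. The direction does not depend on the particular values chosen. The result understates maturation and does not by itself show regression. It should be corrected because the correction is simple and uses scores already collected.

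**What to change.** In SAP 5.7, with a matching exception in 5.16:

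- For each domain, once stage 5 is recorded, count it as 5 at later scheduled Tanner visits, only while the subject remains in the period being summarised (active, withdrawal or re-treatment).
- In each by-visit table show the number assessed and, separately, the number not assessed because maturation was complete.
- Make mandatory the proportion at stage 5 by age at measurement, using the same rule.
- State that the last recorded score decides whether a subject aged 18 or over is due assessment.

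The cost is one derivation rule, one extra count and one table. It needs no new visits or data and changes nothing clinical. The small downside is that a stage 5 recorded in error would persist.

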6.1.1.2. Active Treatment Period – Month 3 to Month 96 Visits

For subjects in the active treatment period, study visits will be scheduled at the study site at Months 3, 6, 9, 12, 15, 18, 21, 24, 27, 30, 33, 36, 39, 42, 45, 48, 51, 54, 57, 60, 63, 66, 69, 72, 75, 78, 81, 84, 87, 90, 93, and 96 (within ± 14 days of the projected visit date based on the actual baseline visit date).

The following safety and efficacy evaluations will be performed at all visits during the active treatment period unless otherwise indicated:

1. Collect/update contact information, including primary care physician or other treating physician.
2. Concomitant medications (DMARDs, corticosteroids, NSAIDs, and anti-infective agents) and non-drug treatments received due to an adverse event.
3. Physical examination (performed by a physician at months 12, 24, 36, 48, 60, 72, 84, and 96 only).
 - The physical examination will include completion of the Tanner Assessment for subjects < 18 years or who have a score of < 5 on 1 or more applicable domain(s).
4. Vital signs: Temperature, blood pressure (mmHg) and pulse rate (beats/min, after sitting for at least 5 minutes).
5. Height (cm, at months 12, 24, 36, 48, 60, 72, 84, and 96 only).
6. Weight (kg):
 - For subjects who are < 18 years of age and who weigh ≤ 62 kg (at all visits).
 - For subjects who are ≥ 18 years of age or weigh > 62 kg (at months 12, 24, 36, 48, 60, 72, 84, and 96 only).
7. Laboratory evaluations (ie, hematology, blood chemistry, and CRP, at months 6, 12, 18, 24, 30, 36, 42, 48, 54, 60, 66, 72, 78, 84, 90, and 96 only). Additional testing may be performed according to local guidelines or standard of care and for follow-up of abnormal laboratory test results.
8. For female subjects, evaluate childbearing potential. The evaluation must be documented in the subject's source documents.
9. Female subjects who, in the opinion of the investigator, are of childbearing potential will have a urine pregnancy test at each visit; this includes subjects who are

- menstruating at the time of the visit. For these subjects, a negative test result must be available before dispensing and/or administration of investigational product. Pregnancy tests will also be done whenever one menstrual cycle is missed during the active treatment period or when potential pregnancy is otherwise suspected. Pregnancy tests may also be repeated as per request of IRB/IECs or if required by local regulations.

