5.8. Growth Parameters

Height, weight, and body mass index (BMI) will also be compared with data from standardized growth charts. Height, weight, and BMI will be summarized using Z-scores. Z-score is calculated using the following formulation:

$$Z = \frac{(X / M)^L - 1}{LS}, L \neq 0$$

Or

$$Z = \ln(X / M) / S, L = 0$$

where X is the physical measurement (eg, height, weight, BMI) and L, M, and S are the values from standardized growth charts provided by the US Centers for Disease Control website (<http://www.cdc.gov/GrowthCharts/>) by gender for children from birth to 240 months. The Z-score cannot be calculated if age > 240 months.

These summaries will be performed for FAS (active period (both parent and extension studies)), WAS and RTAS.

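### Between annual extension visits only under-18s at or below 62 kg are weighed, yet SAP 5.7 and 5.8 do not set those rows apart, so mean weight reads low there, mainly for older children

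*SAP*

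**What the plan says.** **Collection.** Footnote k of the protocol's active-treatment Schedule of Activities states: "Weight will be measured at every visit for subjects who are < 18 years of age and who weigh ≤ 62 kg". For everyone else, "weight will be measured annually as part of the physical examination". Protocol 6.1.1.2 repeats this: "For subjects who are ≥ 18 years of age or weigh > 62 kg (at months 12, 24, 36, 48, 60, 72, 84, and 96". The same rule appears for the withdrawal period (schedule footnote k, section 6.1.2.2) and the re-treatment period (schedule footnote l, section 6.1.2.3).

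**Analysis.** SAP 5.7: "Height, weight, BMI, and Tanner scores will be summarized using the number of observations, mean, standard deviation, median, minimum, and maximum by age group". The groups are 2-4, 5-11 and 12-17 years, fixed at the start of the parent study. The visits shown are the parent baseline, then "weeks 12, 24, 48, and 96, from the parent study and all visits from the extension study", with a closing qualifier that limits this to visits with data. SAP 5.8: "Height, weight, and BMI will be summarized using Z-scores". It names no visits and stops Z-scores at 240 months of age. Both sections cover the active period, the withdrawal set and the re-treatment set. SAP 5.16 does not impute missing endpoints.

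Growth parameters are a secondary endpoint (Protocol 2.2.3), and Protocol 9.4.2 compares them with growth charts. Neither document labels the interim weight rows as a subset.

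**The concern.** The 62 kg and 18-year limits match the boundary between weight-based and fixed dosing in Protocol section 5, so the rule makes sense for supplying drug. It does not suit a growth table. At a scheduled non-annual visit, whether a subject contributes a weight depends on that subject's weight and age. Annual rows hold the whole group and the rows between hold its lighter, younger part. A by-visit table would then alternate between two populations, falling after each annual visit and recovering at the next purely because of who was weighed. For a long-term paediatric safety study, a spurious dip in weight or weight-for-age is a misleading safety signal.

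**Working it through.** The plan states no weight figure, so there is nothing to reproduce. The check counts the affected rows and then sizes the shortfall under stated assumptions.

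**1. Rows.** Active-period visits run every 3 months to Month 96: 96/3 = 32, of which 96/12 = 8 are annual and 32 - 8 = 24 are not. Withdrawal-period visits are Months 1, 3, 6 and 9 (4), Months 12 to 90 every 6 months (14) and Month 96 (1): 19 in all, 8 annual and 11 not.

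**2. Effect of the age limit by group.** 96 weeks is 96 x 7/365.25 = 1.84 years.
- 12-17: the youngest enters the extension at about 12 + 1.84 = 13.84 years and turns 18 after (18 - 13.84) x 12 = 49.9 months. Non-annual rows before that are Months 3, 6, 9, 15, 18, 21, 27, 30, 33, 39, 42 and 45, which is 12. The 12 from Month 51 to Month 93 are empty.
- 5-11: the oldest also enters at just under 13.84, so before about Month 50 only the 62 kg limit removes anyone.
- 2-4: the oldest enters at just under 5 + 1.84 = 6.84 and ends at 14.84, so the age limit never applies.

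**3. Shortfall from the 62 kg limit among minors.** With weights normal (mean m, SD s) and c = (62 - m)/s, the share weighed is Phi(c) and the row mean is low by s x phi(c)/Phi(c). The values of m and s are assumptions.

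| m, s (kg) | c | share weighed | low by (kg) |
|---|---|---|---|
| 55, 12 | 0.58 | 72% | 5.6 |
| 60, 13 | 0.15 | 56% | 9.1 |
| 65, 14 | -0.21 | 42% | 13.1 |

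For the first line, 12 x 0.3365/0.7202 = 5.6, so a true 55.0 kg reads 49.4. Over m = 45 to 65 and s = 8 to 15 the shortfall runs from 0.3 to 13.9 kg. On the Z scale, if 62 kg lay at Z = 0, +0.5 or +1, a true mean of 0 would read -0.80, -0.51 or -0.29.

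**4. Full rule by group.** This simulation keeps a subject in a row if under 18 and at or below 62 kg three months earlier. It uses a lighter and a heavier assumed growth curve, identified here by the full-group mean. Entries are lighter / heavier; differences were taken before rounding.

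| Group, row | Full-group mean (kg) | Weighed | Shortfall (kg) | Mean Z of those weighed (full group about 0) |
|---|---|---|---|---|
| 12-17, Month 3 | 55.4 / 64.5 | 55% / 36% | 4.0 / 11.4 | -0.27 / -0.68 |
| 12-17, Month 12 (annual) | 56.5 / 66.1 | all | 0 / 0 | 0 / 0 |
| 12-17, Month 33 | 58.1 / 68.4 | 18% / 10% | 5.1 / 14.2 | -0.40 / -0.90 |
| 5-11, Month 3 | 35.1 / 38.9 | 100% / 96% | 0.1 / 1.2 | -0.01 / -0.06 |
| 5-11, Month 45 | 47.7 / 54.3 | 93% / 75% | 1.6 / 6.3 | -0.12 / -0.33 |
| 5-11, Month 93 | 56.6 / 66.2 | 40% / 26% | 4.7 / 12.7 | -0.29 / -0.74 |
| 2-4, Month 57 | 32.9 / 36.3 | 100% / 100% | 0.0 / 0.1 | 0.00 / -0.01 |
| 2-4, Month 93 | 44.8 / 50.4 | 98% / 88% | 0.4 / 2.8 | -0.04 / -0.20 |

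In the 12-17 group at Month 3, 35% are absent for age and 10% / 29% for weight, so the raw shortfall mixes both limits. Selection on age alone lowers raw weight but does not move mean Z unless Z varies with age.

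**5. BMI.** Protocol 6.1.1.2 measures height annually, so the active period has no same-visit BMI at interim visits. As they read, the withdrawal schedule also marks height at Months 18, 30 and so on, and the re-treatment schedule at Months 3, 6 and 9, whereas sections 6.1.2.2 and 6.1.2.3 make height annual only. Any BMI computed at those visits would share the problem.

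**The case against.** Several counter-arguments have force.

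- *The SAP already ties rows to collected data.* It does, but the qualifier removes visits with no weights, not visits where weights come from a selected subset.
- *The number of observations is reported, and complete annual rows of raw weight sit alongside.* A reader would see n drop, but would not learn that the missing subjects are the heavier and older ones.
- *SAP 5.8 names no visits, and windowing rules are in a separate specification (SAP 5.1).* By-visit Z-score tables are therefore an inference. The point on 5.8 is only that nothing excludes interim weights.
- *Others may enter interim rows.* Protocol 6.1.4 and 6.1.5 list weight at early-withdrawal and re-treatment assessment visits without an age or weight limit. If windowed into an interim row, a few heavier subjects would appear. Subjects who have just crossed 62 kg may too, since selection works in practice on last known weight. This softens the effect without removing it.
- *The summaries are descriptive.* There is no test or comparator, SAP 5.7 plans no change from baseline for weight, and the primary malignancy endpoint is untouched. That limits the consequence.

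A reader might infer that the tables would show weight suppressed at most visits for the whole cohort. The documents do not support that. Half of the 12-17 group's interim active-period rows are empty rather than biased, and SAP 5.7 tabulates the youngest children, who are almost all weighed for years, separately.

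**Conclusion.** The concern holds for extension-period weight at scheduled non-annual visits, and for weight Z if interim values are used. The direction follows from the collection rule: rows read low wherever some minors exceed 62 kg. The size does not come from the documents; every kilogram and Z figure rests on an assumed weight distribution. Under those assumptions the effect is material for the 12-17 group at the 12 interim active-period rows up to about Month 50, grows through the later rows of the 5-11 group, and is negligible for ages 2-4 until the last years.

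Three further inferences should be avoided. Annual Z-score rows are not complete, because subjects leave at 240 months. Parent-study rows cannot be called either sound or selected, because the documents do not say who was weighed at those visits. BMI is at risk only where it is computed at a non-annual visit.

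**What to change.** In SAP 5.7 and 5.8, base the extension-period by-visit summaries of weight, BMI and their Z-scores on the extension, withdrawal and re-treatment baselines and the annual visits, where all subjects are weighed, noting that Z-scores still end at 240 months. Put any non-annual rows in a separate table labelled as subjects under 18 and at or below 62 kg, with a note that they are not to be read as a trend against annual rows. Leave the parent-study rows as planned. Reconcile the height entries in the withdrawal and re-treatment schedules with Protocol 6.1.2.2 and 6.1.2.3.

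The cost is a short SAP edit and a table footnote, with no change to data collection. The main tables lose rows, including near-complete interim rows for the youngest group; the labelled subset table keeps them.
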